Overview of the Research Setting, Design, and Procedures for the Trial. The trial was conducted in the Baltimore City Public Schools (BCPS) which serves a predominantly African American population--84% of which are eligible for free or reduced lunch. We carried out a school-based, group-randomized trial (GRT) to determine whether the PATHS to PAX + Incredible Years arm yielded superior student and teacher outcomes, relative to the PATHS to PAX Alone arm. We also tested whether the PATHS to PAX + Incredible Years and the PATHS to PAX Alone arms both yielded superior student and teacher outcomes relative to the control arm. These comparisons with the control arm were only carried out to insure that in the case of no significant differences between the two active intervention arms the reason was not because both interventions failed to yield superior outcomes relative to the control arm. A GRT was required given randomization occurred at the level of the school. Four consecutive cohorts of 12 elementary schools for a total of 48 schools were randomly assigned to 1 of 3 conditions: 1) Control; 2) GBG+PATHS Alone; or 3) GBG+PATHS+IY. We confined the study to K-2 teachers given evidence from our most recent trial that the GBG is most effective in K-2.

We also recruited approximately ~ 25 K-2 students per school assigned to the GBG+PATHS+IY condition for participation in the ***IY child and parent groups*** across the four cohorts. Students were selected for inclusion in the IY intervention based on teacher completion of a checklist version of the Oppositional Defiant and Conduct Disorder modules of the teacher version of the Computerized-Diagnostic Interview Schedule for Children IV (C-

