DISC IV). Those students who were sub-syndromal (falling just below the threshold number of symptoms/behaviors to meet DSM-IV diagnostic criteria for Oppositional Defiant or Conduct Disorder) and those who met diagnostic criteria for one or both of these disorders were recruited for inclusion in the IY groups. Randomization. The 12 schools making up each cohort were rank ordered based on school characteristics obtained from prior year archival records, including % Black, % free or reduced lunch, % males, % disciplinary removals, % receiving special education, number of students, and mean levels of standardized achievement scores. Schools adjacent in rank were grouped into triads, or sets of 3. Schools were then randomized to the 3 conditions from within these matched sets of 3. Timing of the Assessments. Classroom observations of student behavior, peer nominations, and child perceptions of peer acceptance were gathered in the fall (October) and spring (May) of the first year for each cohort, whereas teacher ratings of student behavior were gathered in the fall (October) and spring (May) of the first year for each cohort and at 1-year follow-up in Year 2 for each cohort.

Statistical Analysis Plan

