Aims 1 & 2. Outcome Analyses. Trials Aims 1 and 2 were centered on testing whether the PATHS to PAX + Incredible Years arm yielded superior student and teacher outcomes relative to the PATHS to PAX Alone arm. We also tested whether the PATHS to PAX + Incredible Years and the PATHS to PAX Alone arms both yielded superior student and teacher outcomes relative to the control arm. These comparisons with the control arm were only carried out to insure that in the case of no significant differences between the two active intervention arms the reason was not because both interventions failed to yield superior outcomes relative to the control arm. The General Linear Mixed Model was employed given teachers were nested within schools and students nested within teachers and repeated observations nested in both. The General Linear Mixed Model is appropriate when there are multiple sources of random variation and all sources are distributed Gaussian. Murray and colleagues report that even in the case of violations of the Gaussian distribution assumption, the General Linear Mixed Model provides the same Type 1 error protection as the Generalized Linear Mixed Model^{47,48}. Importantly, Aims 1 & 2 outcomes included pre-test-post-test only (e.g., classroom observations, peer nominations, and teacher reported self-efficacy and burn out), pre-test, post-test and 12-month follow-up (e.g., teacher reports of student behavior). General Linear Mixed model analysis of covariance was used in the case of the pre-test-post-test, and pre-test and 1-year follow-up outcomes. In addition to intervention status, the baseline level of the outcome variable was included as a covariate. School was treated as a random effect. Given all the comparisons between conditions were planned and directional, no correction was made for the experiment-wise level of error since such a correction would have only been appropriate in the case of exploratory analyses. Results reported in the Outcome Measures section include the adjusted post-test means and standard errors for the planned comparisons between the 2 intervention arms and between the intervention and control arms.

References

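### Schools were randomised within 16 matched triads, but the described model has no triad or cohort term; if matching predicts outcome beyond baseline, tests of arm differences are conservative.

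*Combined protocol and SAP*

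**What the plan says.** Study Design, Overview of the Research Setting, gives the size and structure: "Four consecutive cohorts of 12 elementary schools for a total of 48 schools were randomly assigned to 1 of 3 conditions". The unit of randomisation is explicit: "A GRT was required given randomization occurred at the level of the school".

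The Randomization paragraph describes the matching. "The 12 schools making up each cohort were rank ordered based on school characteristics obtained from prior year archival records"; these cover racial composition, free or reduced lunch, sex, disciplinary removals, special education, school size and achievement. Schools next to each other in rank formed triads, and "Schools were then randomized to the 3 conditions from within these matched sets of 3".

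The Statistical Analysis Plan, Aims 1 & 2, specifies a General Linear Mixed Model analysis of covariance: "In addition to intervention status, the baseline level of the outcome variable was included as a covariate. School was treated as a random effect". Its account of nesting mentions schools, teachers, students and repeated observations. Triad, cohort and the ranking variables do not appear. On reporting, it says: "Results reported in the Outcome Measures section include the adjusted post-test means and standard errors for the planned comparisons".

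**The concern.** Randomising within triads puts one school from each triad in each arm, so differences between triads cancel out of every arm comparison. The benefit is real whatever model is fitted. The analysis takes credit for it only if the model separates triad variation from the remaining school variation. The described model leaves both in a single school component, so the estimated standard error of an arm difference reflects variation that the contrast does not contain.

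This matters here for two reasons. The standard errors of the planned comparisons are the stated results. The plan also attaches meaning to a non-significant main comparison: the control contrasts are there to explain what happened "in the case of no significant differences between the two active intervention arms". A conservative test makes that outcome more likely, and part of an apparent null could be lost power.

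**Working it through.** **Inputs from the documents.** 4 cohorts × 12 schools = 48 schools, which matches the stated total. 12 / 3 = 4 triads per cohort, so 4 × 4 = 16 triads and 48 / 3 = 16 schools per arm. The figure of 16 triads is not printed but follows directly.

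**Assumptions.** The documents give no ICC, SD, between-triad variance, alpha, sidedness or degrees-of-freedom method. I take a two-sided 5% test on school-level t degrees of freedom, all 48 schools contributing, and an illustrative effect of 0.8 school-mean SD. Let p be the share of residual school-mean variance, after baseline adjustment, that lies between triads. Total residual variance is set to 1.

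**Standard error.**
- True variance of an arm difference: 2(1 − p)/16. The true SD is √(2/16) = 0.354 at p = 0 and √(1.6/16) = 0.316 at p = 0.2, whichever model is fitted.
- Variance estimated without triad: 2/16 on average.
- Overstatement of the SE: 1/√(1 − p).

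**Degrees of freedom.** Without triad: 48 − 3 = 45, t = 2.0141. With fixed triad: (16 − 1) × (3 − 1) = 30, t = 2.0423. Ratio of confidence-interval widths, with triad to without: (2.0423/2.0141) × √(1 − p).

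**Break-even.** p = 1 − (2.0141/2.0423)² = 0.027. Above this the block narrows the interval.

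**Results** (type I error and power from 200,000 simulated trials of school means per setting):

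| p | SE overstated | Type I error, no triad | Power, no triad | Power, fixed triad | CI width ratio |
|---|---|---|---|---|---|
| 0 | 0% | 4.9% | 59.9% | 59.0% | 1.014 |
| 0.1 | 5% | 3.9% | 60.6% | 63.6% | 0.962 |
| 0.2 | 12% | 3.0% | 61.2% | 68.7% | 0.907 |
| 0.3 | 20% | 2.1% | 61.8% | 74.4% | 0.848 |

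With triad as a fixed block, type I error stays at about 5% throughout.

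**How large p could be.** School means also carry student and teacher sampling error, which triads cannot explain. If half of the variance is such noise (an assumption), break-even requires triads to explain 0.027/0.5 ≈ 5.5% of true between-school variance, and p = 0.2 requires 0.2/0.5 = 40%.

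**What baseline adjustment absorbs.** A separate simulation (20,000 trials per setting) put a school-level baseline in the model. With triads holding 30% of post-test school variance, type I error without triad was 1.5%, 2.3% and 3.2% when the triad parts of baseline and post-test correlated 0, 0.5 and 0.8. With a 50% share and a correlation of 1.0 it was 4.3%. Baseline reduces the conservatism, and may remove most of it.

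**Cohort term alone** (42 df, total share 0.2). Power goes from 61.2% to 62.2% if the variance lies between triads within cohorts, from 61.9% to 65.8% if it is split evenly, and from 63.1% to 69.7% if it all lies between cohorts.

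**The case against.** The strongest reply is that the described test is valid and its loss unknown. The October baseline of each outcome is already in the model, so what matters is only what matching adds beyond it. For outcomes such as teacher self-efficacy and burnout, nothing in the documents shows that school demographics, discipline or achievement add anything. That stands, and it is why p is defined after baseline adjustment and the range includes zero.

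Three further points stand as limits.
- The inflation applies to differences between arms. Standard errors of single-arm adjusted means are not inflated in this way (simulated 0.249 from the model against 0.249–0.250 true). The reporting sentence could be read as covering either kind, though it ties the standard errors to the planned comparisons.
- The comparisons are called directional without saying whether tests are one-sided, and no degrees-of-freedom method is given. With a normal reference instead of t, type I error is about 5.7% at p = 0 and 4.4% at p = 0.1.
- The plan is a short summary written in the past tense. A triad term may have been fitted and not mentioned, and replacing completed contrasts with a different model would be a retrospective change that must be declared.

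It can also be said that a fixed block costs more if schools drop out. If two to six triads each lost one school, the penalty at p = 0 would be roughly 3% to 6% and break-even p roughly 0.05 to 0.11. The documents report no school losses, so this is only a sensitivity. None of these points changes the direction of the error or supplies a reason for omitting the factor used to randomise.

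**Conclusion.** The concern holds for the model as described. The analysis omits the blocks within which schools were randomised, and if those blocks predict outcome beyond baseline, the standard errors of arm differences are overstated and the tests conservative. The consequence is lost power and wide intervals, without bias in the contrasts or extra false positives. Over the assumed range p = 0 to 0.3, the overstatement runs from 0% to 20%, and the power change from adding triad runs from about −1 to +13 points at the illustrative effect. Where in that range the trial lies cannot be determined from the documents. It should be fixed because the remedy is cheap and the main comparison rests on 48 schools; confidence in the practical size is only moderate.

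**What to change.** First, state whether triad or cohort was in the fitted model, and give the degrees-of-freedom method and the sidedness of the tests.

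If triad was not fitted, add to the model text:

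> Matched triad (16 levels, which also carries cohort) is included as a fixed block in every student and teacher outcome model; arm contrasts are tested on about 30 school-level degrees of freedom, (16 − 1) × (3 − 1).

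Report the arm contrasts from that model, and declare the change if results have already been produced. If the model without triad stays primary, give the reason and report the triad model as a sensitivity analysis.

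A random triad effect is an alternative. When the triad variance was truncated at zero (an approximation to a fitted random effect), it gave type I error of 5.6% at p = 0 and 5.2% at p = 0.1, so the fixed block is safer. A cohort-only term is a weak fallback that helps mainly if the variance lies between cohorts.

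The cost is one model term and a rerun, since triad and cohort are known for every school. If matching explains nothing, the price is 15 degrees of freedom (45 to 30), an interval about 1.4% wider and about one point of power.

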Our IES funded trial of the GBG+PATHS--or as we refer to it from hereon as PATHS to PAX--featured a group-randomized design, wherein 27-schools (grades K-5) were assigned to one or 3 conditions: 1) Comparison/Control; 2) GBG Alone; or 3) PATHS to PAX (GBG+PATHS). Approximately, 300 teachers and 5,000+ students participated in the trial and provided data, which included classroom observations and teacher ratings of student behavior at pre- and post-test over a 1-year period. The evidence from this group randomized trial, which was completed in 2012, suggested that PATHS to PAX resulted only in modest improvement over the GBG Alone in terms of aggressive/disruptive behavior and teacher outcomes (e.g., perceived behavior management self-efficacy)³⁴.

The Need for Research on the Combination of Evidence-based Universal, Indicated and Treatment Interventions. The relatively modest improvements found for PATHS to PAX (GBG+PATHS) over the GBG Alone served in part as the impetus for our testing the nesting of indicated and treatment interventions within our universal intervention: PATHS to PAX. Also moving us to evaluate such an integration was that despite evidence of long-term benefits of the GBG in terms of the reduction of antisocial behavior and drug use^{10,12} in our 1st and 2nd generation JHU PIRC trials, closer analyses of these data suggest that about half of those children in the highest trajectory of aggressive/disruptive behavior from grades 1-7 demonstrated no GBG impact in the short or long term¹¹. In addition, based on individual interview, focus group, and questionnaire data from our PATHS to PAX trial, the primary reason teachers gave for not implementing PATHS to PAX was because it did not prove helpful with their most aggressive/disruptive students. This was consistent with Han & Weiss' model³⁵ of the factors influencing teacher implementation of evidence-based interventions in school settings. More specifically, Han & Weiss³⁵ argue that teacher perception of the effectiveness of an intervention is a central factor in their level of its implementation. Relatedly, data from our PATHS to PAX trial suggested that the greater the number of highly aggressive/disruptive children in a PATHS to PAX classroom at baseline, the lower the level of teacher implementation of the GBG and PATHS.

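### The SAP justifies its mixed model by students nested in teachers but names only a school random effect; arm tests stay valid, but student-outcome contrasts may lose a little precision

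*Combined protocol and SAP*

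**What the plan says.** The Statistical Analysis Plan (Aims 1 & 2. Outcome Analyses) opens its model description with the data structure: "The General Linear Mixed Model was employed given teachers were nested within schools and students nested within teachers and repeated observations nested in both". It adds a general remark on the method: "The General Linear Mixed Model is appropriate when there are multiple sources of random variation and all sources are distributed Gaussian".

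The analysis itself is a mixed-model analysis of covariance at post-test, and at 1-year follow-up where there is one. Its fixed part is given as: "In addition to intervention status, the baseline level of the outcome variable was included as a covariate". Its random part is one sentence: "School was treated as a random effect".

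On the design, the Overview under Study Design says: "A GRT was required given randomization occurred at the level of the school". It also gives the number of units: "Four consecutive cohorts of 12 elementary schools for a total of 48 schools were randomly assigned to 1 of 3 conditions". The Randomization paragraph there describes allocation within matched sets of three, so each arm has 48 / 3 = 16 schools.

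**The concern.** Of the levels used to justify the model, repeated observations are handled by the baseline covariate and schools by the random effect. The teacher level has no named term, and nothing says one was considered and dropped.

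Students with the same teacher share a classroom and, for teacher ratings, a rater. A school-only model treats them as independent given school. Two things follow when the layout is unequal. Within a school, large classes count for more than they should, because students are averaged rather than classes. Between schools, the weights depend only on the student total and ignore how those students are divided into classes.

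The main question compares the two active arms, with 16 schools in each. Only about 25 students per school in the combined arm were to be recruited to the Incredible Years groups, so an effect averaged over all K-2 students is diluted. The plan expects that this comparison may show no difference and uses the control arm to help interpret that. Avoidable imprecision makes such a result more likely and harder to read.

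**Working it through.** **Inputs.** The documents give 48 schools, 16 per arm, and several K-2 classes per school. They give no student sample size, intraclass correlation, standard error or power, so there is no planned figure to reproduce. Class layout is assumed from the earlier trial in 27 K-5 schools (Rationale, 3rd Generation trial: "Approximately, 300 teachers and 5,000+ students participated in the trial and provided data"). That gives 300 / 27 = 11.1 teachers per school, about 5.6 for K-2 if half the grades hold half the teachers, and 5,000 / 300 = 16.7 students per teacher. Total variance, read as baseline-adjusted, is set to 1 and split into school share s, teacher share t and residual e = 1 - s - t. All shares and spreads below are assumptions.

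**Formulas.** For a school with class sizes n and N students in total:
- True variance of the student-count mean: s + t·Σn²/N² + e/N.
- School weight in the school + teacher model: 1 / (s + 1/Σ[n/(e + n·t)]).
- School weight in the school-only model: 1 / (a + b/N), where a and b are the school and residual variances that model settles on.

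**Balanced case.** Take 6 classes of 18, s = 0.02, t = 0.20. Then Var = 0.02 + 0.20/6 + 0.78/108 = 0.0606, and the SE of the contrast is √(2/16 × 0.0606) = 0.087. Both models give this value, so the ratio is 1.000.

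**Why imbalance matters within a school.** For three classes of 12, 18 and 24, Σn²/N² = (144 + 324 + 576)/54² = 0.358, against 1/3 = 0.333 if classes counted equally. The teacher part of the variance is larger by 0.358/0.333, or 7%.

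**Why imbalance matters between schools.** Take s = 0.03, t = 0.20, e = 0.77, with schools spread evenly over 3 to 9 classes of 17. In the full model a school's variance is 0.03 + (0.20 + 0.77/17)/k for k classes: 0.1118 at k = 3 and 0.0573 at k = 9, a weight ratio of 1.95. The school-only model settles at about a = 0.065 and b = 0.938. Its weight ratio is (0.065 + 0.938/51)/(0.065 + 0.938/153) = 1.17. The school component has absorbed teacher variance and pulled the weights towards equality. The cost of this alone is 2.8% in variance, 1.4% in SE; at t = 0.08 it is 0.8% in variance.

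**Full layouts.** SE of the contrast, school-only divided by school + teacher, 16 schools per arm:

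| Layout | s = 0.05, t = 0.05 to 0.20 | s = 0.02, t = 0.05 to 0.20 |
|---|---|---|
| Balanced, 6 classes of 18 | 1.000 | 1.000 |
| Moderate, 3-9 classes of 12-24 | 1.002 to 1.014 | 1.005 to 1.025 |
| Strong, 2-12 classes, size mean 18, SD about 10 | 1.009 to 1.052 | 1.018 to 1.086 |

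With t = 0 the ratio is 1.000 in every layout. With s near 0 and t = 0.30 it reaches 1.057 (moderate) and 1.18 (strong).

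**Power.** The SAP states no alpha; two-sided 0.05 is assumed here. At s = 0.02 and t = 0.20 under moderate imbalance, the effect giving 80% power in the full model is (1.960 + 0.842) × 0.0881 = 0.247. The school-only power is Φ(0.247/0.0903 - 1.960) = 78%. Under strong imbalance, with SEs 0.0867 and 0.0942, it is 73%.

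**Validity.** In all these layouts the school-only model's own SE was 0.998 to 1.000 of its true SE.

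**With the baseline covariate.** Simulated analyses of covariance (48 schools, 3-9 classes, t = 0.20, s = 0.03) gave mean SE ratios, now school + teacher divided by school-only, of 0.972-0.978 for classes of 11-22 and 0.945-0.955 for classes of 4-28. At t = 0.08 the ratio was 0.992. Type I error was 4-6% under both models. In one unfavourable case, with October-May correlation 0.9 between teachers and 0.5 between students, the SE ratio was 1.008-1.021 and the empirical variance rose by 2-4%. There the single baseline slope moves towards the within-class slope and adjusts less well for stable rater differences.

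**The case against.** The strongest reply is that the omission is inferred from silence. The SAP never says school was the only random effect, and its sentence on school may record only that the randomized unit was random rather than fixed. That stands: the point is that a teacher term is not specified, not that it is known to have been left out.

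A reader might go further and infer that ignoring classes understates the standard errors and inflates type I error. The documents do not support this. Randomization was by school and school is random, so the school component picks up the class variance, as the SE check shows.

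The size is also open to challenge. Every variance share and class spread is assumed, the class counts come from a different trial, and the gain can be slightly negative. This stands, and it is why the size is given as a range.

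Reweighting could change what is estimated if the effect varies with school size, since the full model gives larger schools more weight. The school-only model also carries an implicit weighting, so this argues for showing both results rather than for keeping one.

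Finally, it is tempting to say that the 1-year rating comes from a new teacher. Timing of the Assessments says only that ratings were repeated at 1-year follow-up in Year 2. A change of teacher is plausible but not stated. Year-2 classes form after randomization and need not nest in the randomized school if pupils move.

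**Conclusion.** The concern holds as a modest point about precision and specification. The SAP's reason for a mixed model includes a teacher level that its stated model does not carry. Any loss needs both non-zero teacher variance and unequal classes or schools; without either it is exactly zero. For school shares of 2-5% and teacher shares of 5-20%, it is about 0-3% in SE under moderate imbalance and about 1-9% under strong imbalance. Where the full model would have 80% power, this means 78-80% and 73-79% respectively. Larger losses need a school variance near zero with a large teacher variance. A teacher component is most plausible for teacher ratings, where one person rates many students, but the documents give no figure for it. Low to moderate severity.

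**What to change.** For student-level outcomes, state random intercepts for school and for teacher or classroom within school, using the class or rater at the wave being analysed. Test the arm contrasts on school-level degrees of freedom. Keep school alone for outcomes with one record per teacher or class. For the Year-2 ratings, state which class membership applies and how pupils who changed school are handled.

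The SAP is written in the past tense and refers to reported results. If those analyses used school only, refit with the added term and show both sets of contrasts, labelling the refit as added afterwards. If the term was already fitted, one sentence saying so is enough.

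The model statement changes by one line, and the rating teacher should be identifiable because teachers supply the ratings. A refit costs more than a wording change. The statistical price is one more variance parameter and a baseline slope that moves towards the within-class slope, with the 2-4% rise in variance seen in the unfavourable case. If the teacher variance is estimated as zero, the model reduces to school only.
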